Annex 3: Administrative data request fields

At randomisation:

- Plans to cease fostering in the next year (yes/no/unknown)
- Whether family contains at least one child currently referred for crisis (urgent or emergency) care from CAMHS (yes/no/unknown)
- Whether foster family in crisis and on the verge of placement breakdown (yes/no/unknown)
- Expressed interest in WRAP (programme and evaluation consent given) (yes/no)
- Date data provided
- Local authority
- Family ID
- Postal address
- Kinship carers, unrelated foster carers, or friends and family foster carers, or unknown
- Name of fostering agency (or name of this local authority)
- First name of carer 1
- Surname of carer 1
- Unique ID of carer 1
- First name of carer 2
- Surname of carer 2
- Unique ID of carer 2
- Mobile phone number of carer 1, or 'not available'
- Mobile phone number of carer 2, or 'single carer', or 'not available'
- Email address of carer 1, or 'not available'
- Email address of carer 2, or 'single carer', or 'not available'
- Ethnic group of carer 1
- Ethnic group of carer 2
- Gender of carer 1
- Gender of carer 2
- Other adult household member – first name

- Other adult household member – surname
- Other adult household member – unique ID
- Other adult household member – mobile phone number
- Other adult household member – email address
- Other adult household member – ethnic group
- Other adult household member – gender
- Number of foster children currently placed in this foster family? (0+)
- First name of foster child 1
- Surname of foster child 1
- First name of foster child 2
- Surname of foster child 2
- First name of foster child 3
- Surname of foster child 3
- First name of foster child 4
- Surname of foster child 4
- First name of foster child 5
- Surname of foster child 5
- Unique ID of foster child 1
- Unique ID of foster child 2
- Unique ID of foster child 3
- Unique ID of foster child 4
- Unique ID of foster child 5
- DOB of foster child 1
- DOB of foster child 2
- DOB of foster child 3
- DOB of foster child 4
- DOB of foster child 5
- Ethnic group of foster child 1
- Ethnic group of foster child 2
- Ethnic group of foster child 3
- Ethnic group of foster child 4
- Ethnic group of foster child 5
- Gender of foster child 1
- Gender of foster child 2
- Gender of foster child 3
- Gender of foster child 4
- Gender of foster child 5
- Most recent Strengths and Difficulties Questionnaire total difficulties score for foster child 1
- Most recent Strengths and Difficulties Questionnaire total difficulties score for foster child 2
- Most recent Strengths and Difficulties Questionnaire total difficulties score for foster child 3
- Most recent Strengths and Difficulties Questionnaire total difficulties score for foster child 4
- Most recent Strengths and Difficulties Questionnaire total difficulties score for foster child 5

- Date of most recent SDQ score for foster child 1
- Date of most recent SDQ score for foster child 2
- Date of most recent SDQ score for foster child 3
- Date of most recent SDQ score for foster child 4
- Date of most recent SDQ score for foster child 5
- First name of other (non-foster) child 1
- Surname of other (non-foster) child 1
- First name of other (non-foster) child 2
- Surname of other (non-foster) child 2
- First name of other (non-foster) child 3
- Surname of other (non-foster) child 3
- First name of other (non-foster) child 4
- Surname of other (non-foster) child 4
- First name of other (non-foster) child 5
- Surname of other (non-foster) child 5
- Unique ID of other (non-foster) child 1
- Unique ID of other (non-foster) child 2
- Unique ID of other (non-foster) child 3
- Unique ID of other (non-foster) child 4
- Unique ID of other (non-foster) child 5
- DOB of other (non-foster) child 1
- DOB of other (non-foster) child 2
- DOB of other (non-foster) child 3
- DOB of other (non-foster) child 4
- DOB of other (non-foster) child 5
- Ethnic group of other (non-foster) child 1
- Ethnic group of other (non-foster) child 2
- Ethnic group of other (non-foster) child 3
- Ethnic group of other (non-foster) child 4
- Ethnic group of other (non-foster) child 5
- Gender of other (non-foster) child 1
- Gender of other (non-foster) child 2
- Gender of other (non-foster) child 3
- Gender of other (non-foster) child 4
- Gender of other (non-foster) child 5
- First name of fostering social worker
- Surname of fostering social worker
- Email address of fostering social worker

Final data return – child-level data:

- Local authority name [provided by Coram]
- Family ID [provided by Coram]
- Child ID [provided by Coram]
- Randomisation outcome 'refer for WRAP' (intervention) group or 'do not refer for WRAP (control) group [provided by Coram]
- Date of randomisation [provided by Coram]

- Date of birth of child [provided by Coram]
- Gender of child
- Ethnic group of child
- Child's postcode
- Child's legal status
- Child's care status
- Did the child receive WRAP?
- Date of first WRAP session attended
- Number of WRAP sessions attended
- Whether WRAP was received by other members of the household, which members
- Why WRAP did not take place ('refer for WRAP group') or why WRAP did take place ('do not refer' group)? (if applicable)
- SDQ score at randomisation [provided by Coram]
- Date of SDQ at randomisation [provided by Coram]
- Second SDQ score
- Date of second SDQ score
- Version used for second SDQ score
- Number of placements since randomisation (if applicable)
- Nature of second placement (if applicable)
- Reason for first placement change (if applicable)
- Date of second placement change since randomisation (if applicable)
- Nature of third placement change since randomisation (if applicable)
- Reason for second placement change (if applicable)
- Date of third placement change since randomisation (if applicable)
- Nature of fourth placement change since randomisation (if applicable)
- Reason for third placement change (if applicable)
- Referral(s) made to CAMHS since randomisation
- Date of referral(s) to CAMHS (if applicable)
- Reasons for referrals to CAMHS (presenting issues) (if applicable)
- Comments on data (optional)

Final data return – carer-level data:

- Local authority name [provided by Coram]
- Family ID [provided by Coram]
- Child ID [provided by Coram]
- Randomisation outcome 'refer for WRAP' (intervention) group or 'do not refer for WRAP (control) group [provided by Coram]
- Date of randomisation [provided by Coram]
- Number of foster/kinship children in household at randomisation [provided by Coram]
- Number of other (birth) children in household at randomisation [provided by Coram]
- Number of foster/kinship children currently in household
- Number of other (birth) children currently in household
- Reason for changes in number of children in household (if applicable)
- Did the carer receive WRAP?
- Date of first WRAP session attended
- Number of WRAP sessions attended
- Whether WRAP was received by other members of the household, which members

- Why WRAP did not take place (if in 'refer for WRAP group') or why did WRAP take place (if in 'do not refer')
- Has the foster carer ceased fostering? (yes/no/unknown)
- Plans to cease fostering in the next year? (yes/no/unknown)
- Reasons foster carer has ceased fostering/plans to (if applicable)
- Contributing factors
- Comments on data (optional)

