Primary outcome	Carer wellbeing	Warwick Edinburgh Mental Wellbeing Scale (WEMWBS, Tennant et al. , 2007)	Carer via online survey	✓	✓
Secondary outcome(s)	Perceived peer support networks	'How many other local foster carers or kinship carers could you ask for help if you needed it?'	Carer via online survey	✓	✓
	Child mental health	Brief Assessment Checklists for Children and Adolescents (Tarren-Sweeney, 2013)	Foster carer or kinship carer, reporting on all children currently in the household via online survey	✓	✓
	Foster child mental health	Strengths and Difficulties Questionnaire (Goodman, 2001)	Various informants, may be foster carer, social worker or young person via administration data request	✓	✓

	Family relationships	SCORE-15 (Stratton et al. , 2010)	Foster carer or kinship carer via online survey	✓	✓
	Placement changes	Administrative data: number of placements, dates of placement changes, reasons for placement changes.	Local authority data request		✓
Exploratory outcome(s)	Foster carer turnover	Administrative data: foster carer turnover, reason for foster carer ceasing to be a foster carer.	Local authority data request		✓
	Service use/help seeking	Administrative data: referrals to CAMHS of foster children, dates of referrals, reasons for referrals (presenting issues).	Local authority data request		✓

For the online survey, we have consulted our advisors in finalising our choice of measures for primary data gathering directly from families. Each foster carer completing the survey will be sent a £10 incentive voucher, and we have timed the survey at around 15 minutes to complete. On the final page of the survey, participants will be asked which voucher they want to receive from a choice of two options (we anticipate using Amazon and Love2Shop). Measures will be completed by carers, but the survey will ask carers to answer questions about themselves, their foster children, their kinship children, and their birth children. The online survey includes:

- Questions referring to **foster and kinship carer demographic** information. This includes date of birth, initials, mobile phone number, and email address. We will not ask any further details, as we want to minimise burden and intend to match this data with local authority data using these fields.

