We will request administrative data from local authorities in March 2024. We will follow DfE SSDA903 requirements to the greatest extent possible, to minimise burden. Some data will have the foster child as the unit of analysis, and some will have the carer as the unit of analysis. We will use an Excel template for the data request that will be partially completed with demographic information about carers and children provided at randomisation. This entails routinely collected data on the care status and living arrangements of children, numbers and dates of placement changes, foster carer turnover management information (unique ID of the foster carer and step-down dates), and Strengths and Difficulties Questionnaire (SDQ) total difficulties scores for foster children (and date of the score and the unique ID of the child). We will gather SDQ scores from local authorities in March 2024, which according to published figures should be available for around 84% of looked-after children. A full breakdown of variables is provided in the spreadsheet template in Appendix 2.

For our secondary outcome of **placement changes**, we will seek data on the following variables for each foster child:

1. Number of placements since randomisation

¹⁷ Collins, J., Gibson, A., Parkin, S., Parkinson, R., Shave, D., & Dyer, C. (2012). Counselling in the workplace: How time-limited counselling can effect change in well-being. *Counselling and Psychotherapy Research*, 12(2), 84-92.

¹⁸ Maheswaran, H., Weich, S., Powell, J., & Stewart-Brown, S. (2012). Evaluating the responsiveness of the Warwick Edinburgh Mental Well-Being Scale (WEMWBS): Group and individual level analysis. *Health and Quality of Life Outcomes*, 10(1), 1-8.

¹⁹ Hamilton, E., Carr, A., Cahill, P., Cassells, C., & Hartnett, D. (2015). Psychometric properties and responsiveness to change of 15- and 28-item versions of the SCORE: A family assessment questionnaire. *Family process*, 54(3), 454-463.

2. Date of first placement change since randomisation (if applicable)
3. Nature of second placement (if applicable)
4. Reason for first placement change (if applicable)
5. Other reason for first placement change (if applicable)
6. Date of second placement change since randomisation (if applicable)
7. Nature of third placement (if applicable)
8. Reason for second placement change (if applicable)
9. Other reason for second placement change (if applicable)
10. Date of third placement change since randomisation (if applicable)

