1. Has the foster carer ceased fostering? (yes, no)
2. Why has the foster carer ceased fostering? (resignation, uncontested termination of approval, contested termination of approval, other, unknown)
3. Other reason (if applicable)
4. Contributing factors (e.g. illness)

We will also seek data on referrals to Child and Adolescent Mental Health Services - **CAMHS referrals** - for foster children in the fostering household. From discussions with local authority data leads, it is likely that where this information is centrally stored, it will only be available for foster children in the household and not other children. This analysis will be exploratory only.

While not an outcome variable, we also intend to request data from Barnardo's on **engagement** with the intervention. This will include attendance at information sessions, the number of WRAP sessions attended and the dates of WRAP sessions. The intervention is designed to be self-sustaining, so we will also gather and match in data from Barnardo's on who leads the ongoing Keeping Connected groups. This will allow us to describe the delivery of the intervention in the final report and will be used in the compliance analysis.

Analysis plan

Does the intervention work?

Q1 Analysis

The trial will take an RCT design. The primary outcome will be collected at baseline (for most families, March 2023) and endline (for all families, July 2024). All outcomes will be analysed on an intention to treat basis in that all participants will be analysed according to the trial arm to which they were assigned, as opposed to the service they received.

Families are the unit of randomisation, but data will be analysed at the individual level e.g. individual foster child placement breakdown, individual foster carer turnover, and individual SDQ outcomes for foster children. We will need to account for clustering within our analysis. We may receive two responses from couples. In this case, we will use clustered standard errors to account for this.

We know from prior experience of analysing routinely collected Strengths and Difficulties scores for looked-after children that local authorities do not generally know or collect data on the version of the SDQ used and who completed it (carer, child, or social worker). We therefore anticipate it will be challenging to standardise scores on the SDQ by informant, but will do so if data allows.

Data cleaning

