We will also look at attendance as a proportion of household members (e.g., two out of four household members attending means 0.5 attendance) as an instrumental variable in outcomes, as well as the attendance of children at WRAP sessions in relation to their scores on the SDQ and BAC. We may conduct an exploratory dosage analysis with the number of sessions as the instrumental variable, as opposed to binary non-/attendance.

Analysis of harms

We will analyse the proportion of foster children that demonstrate reliable and clinically significant deterioration between their 'pre' and 'post' SDQ scores. For a clinically significant deterioration we will report the proportion of foster children that move from a pre score of below 17 to above at post-test i.e. the clinical threshold for the SDQ (Goodman, 2001²²; Goodman, Ford, Simmons *et al.*, 2000²³). For reliable deterioration, we will report the proportion of foster children that show an increase in SDQ score from pre to post test that is greater than the reliable change index (Jacobson and Truax, 1991²⁴).

Process evaluation

Evaluation questions

²² Goodman, R. (2001). Psychometric properties of the strengths and difficulties questionnaire. *Journal of the American Academy of Child and Adolescent Psychiatry*, 40(11), pp.1337-1345.

²³ Goodman, R., Ford, T., Simmons, H., Gatward, R., & Meltzer, H. (2000). Using the Strengths and Difficulties Questionnaire (SDQ) to screen for child psychiatric disorders in a community sample. *British Journal of Psychiatry*, 177, pp.534-539.

²⁴ Jacobson, N. S., & Truax, P. (1991). Clinical significance: a statistical approach to defining meaningful change in psychotherapy research. *Journal of Consulting and Clinical Psychology*, 59(1), pp.12-19.

The process evaluation consists of three summative questions under three themes: delivery of the intervention; participant experiences and learning for future delivery:

Delivery of the intervention

- A. To what extent was the intervention implemented as intended compared to the activities detailed in the theory of change and logic model?
- This will consider:
 - What are the core elements of the intervention that was delivered?
 - How does the delivered intervention vary across groups?
 - How is it different to usual support provided to the foster and kinship community?
 - What are the barriers and enablers to successful implementation of WRAP?

Participant experiences

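### Annex 3 asks for the SDQ version of the second score only, so a change of informant between the two scores cannot be identified when the deterioration rules are applied

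*Protocol*

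**What the plan says.** **Who completes the SDQ.** The outcome table under Outcome measures gives the source as "Various informants, may be foster carer, social worker or young person via administration data request". Analysis plan, Q1 Analysis, adds that authorities generally neither know nor record which version was used or who filled it in. The team therefore expects it to be "challenging to standardise scores on the SDQ by informant, but will do so if data allows".

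**What is requested at randomisation (Annex 3).** For each foster child there are two SDQ fields: "Most recent Strengths and Difficulties Questionnaire total difficulties score for foster child 1" and "Date of most recent SDQ score for foster child 1", repeated for children 2 to 5. There is no field for version or informant.

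**What is requested at the end (Annex 3, child-level return).** The first score and its date are pre-filled by the evaluator. The authority adds the second score, its date and "Version used for second SDQ score". The description of the return under Outcome measures lists only the score, its date and the child's identifier.

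**How the scores are used.** Besides being secondary outcome 3b, the SDQ supplies the whole of Analysis of harms. Reliable deterioration is an "increase in SDQ score from pre to post test that is greater than the reliable change index". Clinically significant deterioration is a move from below 17 to above it. Neither rule requires both scores to come from the same version or informant, and neither refers back to the caveat in Q1 Analysis.

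**The concern.** A reliable change index sets its threshold from the measurement error of repeated scores obtained in the same way. If a carer completes the first SDQ and a social worker or the young person the second, disagreement between raters adds variance that the threshold does not cover. A child who has not changed is then more likely to be counted as deteriorated. The cut at 17 has the same weakness.

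The protocol sees the general problem and offers a conditional remedy. The data request defeats that remedy at baseline even for authorities that could answer. A version recorded at one time point cannot show whether the version changed. A later analysis plan cannot repair this, because it cannot use a field that was never requested. What is at stake is the meaning of the harms proportion and the promised standardisation of outcome 3b. The primary outcome, carer wellbeing, is not affected.

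**Working it through.** **Step 1: the fields side by side (Annex 3)**

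| Item | Score at randomisation | Second score |
|---|---|---|
| Total score | requested | requested |
| Date | requested | requested |
| Version | not requested | requested |
| Who completed it | not requested | not requested |

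Q1 Analysis treats version and who completed the form as separate facts. So even for the second score, the informant is known only as far as the version reveals it. Standardising both scores by informant, or sorting pairs into same and different informant, needs the missing baseline entries.

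**Step 2: direction and rough size**

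The protocol states no figure for this analysis, so there is none to reproduce. It also gives no SD, reliability, cross-informant correlation or index multiplier. All of the following are assumptions: bivariate normal scores with equal SDs, no true change, a multiplier of 1.96, reliability r used in the index, correlation ρ between scores from different informants, and mean informant shift d in SD units.

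- Index threshold in SD units: 1.96 × √(2(1 − r))
- SD of the difference for a mixed pair: √(2(1 − ρ))
- Share flagged: 1 − Φ((threshold − d) / √(2(1 − ρ)))

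For same-informant pairs ρ = r and d = 0, so the ratio is 1.96 and the share is 2.5%. For mixed pairs:

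| r | ρ | Threshold | SD of difference | Ratio at d = 0 | Flagged, d = 0 | Flagged, d = +0.25 |
|---|---|---|---|---|---|---|
| 0.70 | 0.6 | 1.518 | 0.894 | 1.70 | 4.5% | 7.8% |
| 0.70 | 0.5 | 1.518 | 1.000 | 1.52 | 6.4% | 10.2% |
| 0.80 | 0.4 | 1.240 | 1.095 | 1.13 | 12.9% | 18.3% |
| 0.85 | 0.3 | 1.074 | 1.183 | 0.91 | 18.2% | 24.3% |

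A shift the other way offsets the effect. At d = −0.25 the first row becomes (1.518 + 0.25)/0.894 = 1.98, or 2.4%, and the last becomes (1.074 + 0.25)/1.183 = 1.12, or about 13%.

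**Step 3: effect on the overall proportion**

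The share of mixed pairs is also unknown. If it were 30%, with d = 0:

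- low end: 0.7 × 2.5% + 0.3 × 4.5% = 3.1%
- high end: 0.7 × 2.5% + 0.3 × 18.2% = 7.2%

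The comparison is 2.5% with no mixing.

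**Step 4: the cut at 17**

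No rate was calculated for this rule. It depends on how many children score near 17, and crossings occur by chance even with one informant. Only the direction carries over: lower agreement between the two scores gives more chance crossings.

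**The case against.** **The obstacle is already acknowledged.** Q1 Analysis says authorities generally do not hold this information. It would therefore be wrong to say that the team overlooked informant mixing, and the missing field bites only where an authority could have answered. That stands. It limits how much the fix can recover, but it does not explain asking for the version at one time point and not the other.

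**No between-arm bias is shown.** A reader might infer that the harms comparison between arms is distorted. Mixing unrelated to allocation raises the proportion in both arms and does not by itself bias the difference. Independence is not guaranteed: the Randomisation section cites 32% of children in care moving placement within a year, a move can change who completes the form, and placement change is itself a secondary outcome. But nothing in the protocol shows that mixing differs by arm.

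**No loss of power is shown.** A reader might also infer that outcome 3b loses power because its baseline adjustment mixes raters. The protocol specifies no such adjustment. Secondary outcomes analysis gives linear regression for child mental health and names no baseline SDQ covariate. The primary model takes only predictors that are significantly unbalanced between arms.

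**The figures are all assumed.** This is correct. They show direction and a plausible range, not an estimate.

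**Other data give a cross-check.** The carer-reported Brief Assessment Checklist is collected at both times, and a correlation with the SDQ is planned. This helps in aggregate but cannot identify a mixed pair.

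**Matching on informant type is imperfect.** A carer score at both times may come from two different carers after a move. That also stands.

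**Conclusion.** The point holds as a gap in the data request. Annex 3 records the version for the second score only and the informant for neither. Baseline scores therefore cannot be standardised by informant, and changed-informant pairs cannot be identified under either deterioration rule.

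With no true change and no average difference between informants, mixed pairs would exceed the reliable change index in roughly 4.5% to 18% of cases, against a nominal 2.5%. The range rests on assumed reliabilities of 0.70 to 0.85 and cross-informant correlations of 0.3 to 0.6. The nominal rate also assumes that the same-informant correlation over the study interval equals the reliability used in the index. A mean shift between informants moves these rates up or down.

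The effect falls on the absolute deterioration proportion, which is the quantity the protocol says it will report. The documents do not support a claim of a biased between-arm difference, lost power for outcome 3b, or any effect on the primary outcome.

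**What to change.** - In Annex 3, request version and informant, each with an unknown option, for both the score at randomisation and the second score. The baseline details can still be collected in the final return.
- Report by arm the share of pairs with matched, differing and unknown informant. In a pilot this is useful information for a full-scale trial.
- Keep the all-pairs proportions for both deterioration rules and show the same-informant proportions beside them. The matched set should not replace all pairs: it may be very small, and leading on it could hide a harm signal.
- Standardise by informant where it is known at both times. Where it is not, state the limitation next to the harms result.
- Do not add a covariate for differing or unknown informant to the model for outcome 3b. The second informant is determined after randomisation, so the model would condition on a post-randomisation variable.

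The cost is three more entries per child (baseline version, baseline informant and second informant) in a template that already asks for the second version. The downside is the one the protocol anticipates: the answer may be unknown for many children.
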